3.2 Aims and Objectives

The three specific aims will be realized in the context of the logic model shown in Fig. 3:

AIM 1: Assess the comparative effectiveness of two effective encounter decision aids (Option Grid and Picture Option Grid) against usual care on shared decision-making (SDM), decision quality, treatment choice and other direct outcomes in women, and differentially by socioeconomic status (SES).

Hypothesis 1. The encounter decision aids will increase SDM in the clinic visit and improve decision quality, knowledge, and quality of life in women of higher and lower SES compared to usual care. We also anticipate that they will reduce decision regret and improve the perceived integration of healthcare delivery (see Fig. 3).

Hypothesis 2. The Picture Option Grid will be more effective than the Option Grid at improving primary and secondary outcomes in women of lower SES. There will be no difference between the effects of the two encounter decision aids in women of higher SES.

AIM 2: Measure the effect of the Picture Option Grid on disparities in decision-making (decision quality, knowledge, and SDM) and treatment choice, and conduct an exploratory analysis of the mediation and moderation effects.

Hypothesis 1. Compared to the Option Grid and usual care arms, the Picture Option Grid will reduce disparities in decision quality, knowledge and participation in shared decision-making between women of lower and higher SES. It is also likely to reduce disparities in treatment choice.

Hypothesis 2. The effect of the Picture Option Grid on treatment choice will be mediated by post-intervention knowledge, shared decision-making, and post-intervention values (reported in 'What Matters Most to You' subscale of DQI, e.g., keeping breast, removing breast to gain peace of mind, avoiding radiation, etc.) (see Fig. 4).

[figure not shown]
Hypothesis 3. For women of lower SES, socioeconomic barriers (e.g., resource constraints, as reported in the Decision Quality Instrument) will affect treatment choice and thereby moderate the intervention's effect.

AIM 3: Explore strategies that promote the encounter decision aids' sustained use and dissemination using a theoretical implementation model.

Hypothesis 1. Pre-visit planning, minimal clinician training, flexibility of use, and integration into the workflow and EMR will facilitate sustained use.

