4.1.1 Design Overview

We will use a three-arm, multi-site randomized controlled superiority trial with stratification by SES and parallel design (Aims 1 and 2). One thousand one hundred patients (half higher SES and half lower SES) will be recruited from four large cancer centers over a 18-month period. Randomization will be at the clinician level, nested within study sites, and will involve data analyst blinding. In preparation for the trial, we will conduct semi-structured interviews in Year 1 with women of lower SES who have completed treatment for early stage breast cancer to adapt the “What Matters Most to You” subscale of the Decision Quality Instrument (DQI) for women of lower SES. For Aim 3, we will use interviews, field-notes, and observations to explore strategies that promote the encounter decision aids’ sustained use and dissemination using a theoretical implementation model. See study Gantt Chart on page 46.

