4.1.2 Randomized Controlled Superiority Trial (Aims 1 and 2)

According to Cooper et al., the most appropriate design for evaluating interventions that aim to eliminate disparities is a classic experimental design with random assignment to experimental and control groups, with measurements of key variables pre- and post-interventions⁸². We have thus chosen to conduct a three-arm, multi-site randomized controlled superiority trial with stratification by SES (high versus low) and randomization at the clinician level (nested within study sites) (see Fig. 5).

Fig. 5. CONSORT* Study Flow Diagram

*CONSORT stands for Consolidated Standards of Reporting Trials, as reported in the CONSORT statement⁸⁷.

At each site, we will use a cross-sectional study design and randomize participating clinicians (three to five clinicians per site) to one of three arms (Picture Option Grid, Option Grid, or usual

care). We will use an R script written by the study statistician to complete the surgeon randomization. At each site, patients who have given informed consent and are seeing one of the participating clinicians will be allocated to the clinician's corresponding arm (Picture Option Grid, Option Grid, or usual care). Approximately the same number of patients in each socioeconomic stratum will be allocated to each arm. We will monitor accrual within each arm for each socioeconomic stratum at each site to ensure that a similar number of patients in each socioeconomic stratum receive each treatment. The total number of patients recruited at each site will be allowed to vary.

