4.5.1 Primary Outcome Measure

The primary outcome measure (see Table 3) is the validated 16-item Decision Quality Instrument (DQI) for breast cancer (see Appendix C), which includes a knowledge subscale⁸⁹. The DQI, designed to be administered post-decision, will be assessed at T2 and T3. It aims to measure the extent to which patients are informed about their options, are involved in the decision-making process, and receive a surgery (mastectomy or BCS) aligned with their values, attitude towards risks, and preferences. It produces three scores: (1) knowledge, (2) concordance, and (3) decision process. Validation demonstrated good feasibility with minimal missing data and good 4-week retest reliability for both knowledge (ICC = 0.70) and concordance (ICC > 0.72). Discriminant validity was acceptable⁸⁹.

Table 3. Outcome Measures According to Data Collection Periods

	TIMEPOINT						
	-T0	T0 Baseline	T1 In-Visit	T2 Post- Visit	T3 1 wk PS*	T4 12 wks PS**	T5 1 yr PS
CONSENT AND ENROLLMENT							
Eligibility Screen	X						
Informed Consent	X						
Allocation (via surgeon confirmation)	X						
INTERVENTIONS							
Arm 1: Option Grid			X				
Arm 2: Picture Option Grid			X				
Arm 3: Usual Care			X				
OUTCOME MEASURES							
Rates of recruitment – documented and tracked in REDCap		X					
Discontinuation rates – documented and tracked in REDCap		X		X	X	X	X
Demographic data – 6 items, self-reported		X					
Health literacy – 1-item Chew's health literacy screening		X					
Decision quality (primary outcome measure) – validated 16-item DQI, subscale adapted for low SES				X	X		

Knowledge – validated 5-item DQI knowledge subscale		X		(X)	(X)		
Treatment intention – self-reported via DQI				(X)			
Treatment choice – obtained from medical records					X		
Quality of life – validated 6-item EQ-5D-5L		X				X	
Anxiety – validated 8-item PROMIS anxiety short form		X		X	X	X	
Shared decision-making (observed) – validated OPTION ⁵			X				
Shared decision-making (self-reported) – validated 3-item CollaboRATE				X			
Decision regret – validated 5-item decision regret scale					X	X	X
Integration of health care delivery – validated 4-item IntegRATE		X				X	
Financial toxicity – four items from validated COST measure and self-report of out-of-pocket medical expenses in the past month					X	X	X
Intervention's patterns of use – questions and photos of intervention				X	X		

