4.8 Analysis

4.8.1 Power Calculation

For Aim 1, hypothesis 1, we base the effect size estimation on published data from randomized controlled trials of decision aids for breast cancer surgery^{32,41,115,116}, suggesting that a reasonable effect size for DQI is 9.34, that the standard deviation between patients in the intervention arms compared to usual care is 12.00, and that a within-physician intra-class correlation (ICC) of 0.05 is reasonable. This ICC is justified because treatment varies within clinic, thereby allowing heterogeneity that occurs between physicians across centers to be blocked. We assume that four physicians will participate in the study at each of the four clinics (at least one assigned to each of the three trial arms at each center) and assume a patient attrition rate of 20%. Under these assumptions, a study of 1,100 participants (68.75 participants per physicians and 366.66 per treatment group) has power of greater than 99.8%

to reject the null hypothesis that the encounter decision aid groups and the control group have equal means, using a two-sided 0.05 level test when the true mean difference is 9.34. Given recruitment difficulties due to seasonal trends in breast cancer diagnoses and a lower number of eligible patients than planned based on the feasibility assessments (see reasons in modification letter), the sample size has been revised to 600 participants. The power will remain above 80% for all primary hypotheses.

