For Aim 2, the power of the test for disparities between higher and lower SES is necessarily lower than the overall test at the same effect size, as four groups are compared (Picture Option Grid higher SES, Picture Option Grid lower SES, Option Grid and usual care higher SES, Option Grid and usual care lower SES). However, because patient SES varies within physician, power can be conservatively computed as if the patient-level variance was doubled and the total number of patients halved. If the true difference in the effect of the Picture Option Grid on DQI between the higher and lower SES groups is 8.5 compared to Option Grid or compared to usual care, the power for a two-sided alpha-level test at the 0.05-level is just above 80%. With a revised sample size of 600 participants, the power is unlikely to reach 80%. However, given those power calculations are resting on assumptions that may not be entirely accurate, we will know once we start the analysis if we have enough power for aim 2 hypotheses with a sample size of 600 participants. A significant finding is even more likely to be obtained if the estimated variability in the data turns out to be much smaller than assumed here. It could indeed be the case with the revised sample size. It is not critical to account for multiple testing because in both the primary (Aim 1) and secondary (Aim 2) analyses, a single pair of groups is compared.

We are assuming an effect size of 9.34 based on past studies of decision aids for breast cancer surgery^{32,41,115}.

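### No DQI score or time point is named primary, and the single-pair reason for not adjusting Aim 1 is wrong and conflicts with the plan's own Scheffe rule, which the power figures ignore

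*Combined protocol and SAP*

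**What the plan says.** **Endpoint.** Section 4.5.1 makes the whole Decision Quality Instrument (DQI) the primary outcome measure. Of the instrument it says "It produces three scores: (1) knowledge, (2) concordance, and (3) decision process", and that it "will be assessed at T2 and T3". Section 4.8.3 analyses each follow-up period separately and allows, without requiring, a longitudinal model. Section 4.5.1 and Table 3 place knowledge inside the DQI. The Section 3.2 hypotheses and Section 4.8.4 list knowledge beside decision quality.

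**Comparisons.** Section 3.2 has both aids improving on usual care (Aim 1, Hypothesis 1). It adds for Hypothesis 2: "The Picture Option Grid will be more effective than the Option Grid at improving primary and secondary outcomes in women of lower SES". The model in Section 4.8.3 can carry two treatment indicators, one for each aid against usual care.

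**Multiplicity.** Section 4.8.1 says: "It is not critical to account for multiple testing because in both the primary (Aim 1) and secondary (Aim 2) analyses, a single pair", meaning one two-group contrast. Section 4.8.3 says that multiple comparisons will be handled by Scheffe's method, and does not say which comparisons form the family. The same section makes SES-stratified analyses depend on a significant SES-by-intervention interaction.

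**Power.** Section 4.8.1 bases power on a difference in DQI "using a two-sided 0.05 level test when the true mean difference is 9.34". At 1,100 patients it gives more than 99.8% for Hypothesis 1, and power above 80% with an ICC greater than 0.19. For Hypothesis 2, with 550 lower-SES patients, it gives 99% at ICC 0.05 and 80% at ICC 0.175. After the reduction to 600 patients it states: "The power will remain above 80% for all primary hypotheses".

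**The concern.** There are three linked problems, the first being the most important.

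1. Nothing fixes which DQI score, composite or time point decides the trial. Two analysts who both followed the text could report different primary results. A Scheffe adjustment among arms does not control that choice.
2. The reason given for not needing adjustment does not describe Aim 1, and it disagrees with the rule in Section 4.8.3. A reader cannot tell whether the lower-SES comparison, the three scores or the two time points fall under that rule.
3. If Scheffe is used, the stated power and the reassurance about higher ICCs belong to a different, less demanding test.

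**Working it through.** **Inputs from Section 4.8.1:** difference 9.34, SD 12.00, ICC 0.05, 16 surgeons (four at each of four sites), 20% attrition, two-sided 0.05, three equal arms.

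**Formula.** With N patients and k surgeons, analysed patients per surgeon are m = 0.8N/k. For one arm against one arm,

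SE = √[2 × 144 × (ICC + (1 − ICC)/m) / (k/3)], and power = Φ(9.34/SE − critical value).

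**Step 1: reproduce the plan at 1.960.**
- Hypothesis 1, N = 1,100: m = 55, SE = 1.906, 9.34/1.906 = 4.900. Power = Φ(2.940) = 99.84% (plan: more than 99.8%). Power is 80% at ICC 0.191 (plan: 0.19).
- Hypothesis 2, N = 550: m = 27.5, SE = 2.137, ratio 4.371. Power = Φ(2.411) = 99.2% (plan: 99%). Power is 80% at ICC 0.176 (plan: 0.175).

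Pooling both aids against usual care is the one reading that would make Hypothesis 1 a single pair. It gives an ICC limit of 0.261, which does not match 0.19. The plan's sum is therefore for one pairwise contrast, unadjusted.

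**Step 2: replace 1.960 by a Scheffe value.** The plan defines no family, so three arms is an assumption. The large-sample value is √χ²(0.95; 2 df) = √5.991 = 2.448. With surgeon-based degrees of freedom it is √[2F(0.95; 2, df)]: 2.759 at 13 df (16 surgeons − 3 arms), 2.918 at 9 df (12 − 3) and 2.680 at 17 df (20 − 3). The df are also assumptions; those results use the noncentral t.

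ICC at which power reaches 80% (16 surgeons, normal):

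| Test | N | Unadjusted | Scheffe |
|---|---|---|---|
| Hypothesis 1 | 1,100 | 0.191 | 0.134 |
| Hypothesis 2 | 550 | 0.176 | 0.117 |
| Hypothesis 1 | 600 | 0.178 | 0.120 |
| Hypothesis 2 | 300 | 0.149 | 0.089 |

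Power at the revised size, ICC 0.05. For Hypothesis 1, N = 600, m = 30, SE = 2.100 with 16 surgeons. For Hypothesis 2, N = 300, m = 15, SE = 2.474.

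| Test | Surgeons, reference | Unadjusted | Scheffe |
|---|---|---|---|
| Hypothesis 1 | 16, normal | 99.4% | 97.7% |
| Hypothesis 1 | 16, 13 df | 98.4% | 93.7% |
| Hypothesis 2 | 16, normal | 96.5% | 90.8% |
| Hypothesis 2 | 16, 13 df | 93.6% | 82.7% |
| Hypothesis 2 | 12, 9 df | 87.9% | 71.7% |
| Hypothesis 2 | 20, 17 df | 96.1% | 88.4% |

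The 12 and 20 surgeons come from Section 4.1.2, which will "randomize participating clinicians (three to five clinicians per site) to one of three arms": 3 × 4 = 12 and 5 × 4 = 20. If site took three further df (16 surgeons, 10 df), Hypothesis 2 would have 79.7%.

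**Step 3: what an unnamed endpoint could cost.** This is a simulated chance of at least one false-positive result for either aid against usual care, with three equal arms and the Scheffe value 2.448. The documents give no correlation between scores or times; 0.7 and 0 are assumed as a range.

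| Results treated as primary | Correlation 0.7 | Correlation 0 |
|---|---|---|
| One score, one time | 2.7% | 2.7% |
| One score, T2 and T3 | 4.7% | 5.4% |
| Three: process at T2 and T3, concordance at T3 | 6.3% | 7.9% |
| Five: adding knowledge at T2 and T3 | 8.9% | 12.8% |
| Six: adding concordance at T2 from stated intention | 10.0% | 15.2% |

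**The case against.** The plan does have a multiplicity rule. Section 4.8.1 says adjustment is not critical; it does not say there will be none, and Section 4.8.3 says multiple comparisons will be accounted for. A reader might infer that Aim 1 will be tested unadjusted, with about 9% error for two aids against usual care. The documents do not support that. With three-arm Scheffe, error is 2.7% for one score at one time and about 5% for one score at both times.

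A reader might also infer that the claim of power above 80% fails at 600 patients. It does not on the plan's own inputs: with 16 surgeons and ICC 0.05, Hypothesis 2 keeps 91% (normal) or 83% (13 df). Values clearly below 80% need fewer surgeons or a higher ICC. The three-arm family is itself an assumption. The SES interaction terms in Section 4.8.3 would permit a wider family, with a different critical value.

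The lower-SES comparison may not always be tested, because Section 4.8.3 gates stratified analyses on the interaction. An error rate that treats that comparison as certain to be performed would therefore overstate the case, and none is given here.

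Knowledge is partly settled: Section 4.5.1 and Table 3 put it inside the DQI. For Aim 2, the power text pools the Option Grid with usual care, so the single-pair phrase has some basis there, and no claim is made about Aim 2.

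These objections narrow the power and error claims. They do not supply a primary score or time point, and they do not reconcile the two multiplicity statements.

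**Conclusion.** The point holds in three parts of unequal weight.

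- **Endpoint (main defect).** No DQI score, composite or time point is named primary. The 6% to 15% error arises only if three to six score and time results are all treated as primary, and rests on the assumed correlations. The ambiguity itself needs no assumption.
- **Multiplicity wording (should be fixed).** The single-pair reason is wrong for Aim 1 and conflicts with Section 4.8.3, whose family is undefined.
- **Power (should be fixed).** The stated figures describe an unadjusted test. If Scheffe covers the three arms, the tolerances of 0.19 and 0.175 become about 0.134 and 0.117, and at the revised size 0.120 and 0.089. Power above 80% survives on the plan's inputs, but for Hypothesis 2 it depends on the number of surgeons: 72% with 12 to 88% with 20.

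**What to change.** Section 4.1.1 says the trial "will involve data analyst blinding". While that blinding holds, and before outcome data are seen by arm:

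1. In Section 4.5.1, name one DQI score, or a composite with its scoring rule, at one time point as primary. The choice is the sponsor's. Make the other scores and times secondary, and state whether knowledge is part of the primary.
2. In Section 4.8.1, replace the sentence that calls adjustment not critical with a reference to the rule in Section 4.8.3.
3. In Section 4.8.3, define the Scheffe family as the three-arm contrasts on that endpoint. Use the same critical value for the lower-SES Picture Option Grid versus Option Grid test. State whether that test is pre-specified or depends on the interaction result.
4. Restate power and the ICC tolerances at 600 patients under that rule, with the actual number of surgeons and the df used, and qualify the above-80% statement accordingly.

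**Cost.** Text in Sections 4.5.1, 4.8.1 and 4.8.3, and no extra patients. Results on other scores and times become supportive. The reported Hypothesis 2 power falls, for example from 96.5% to 90.8% (16 surgeons, normal) or from 87.9% to 71.7% (12 surgeons, 9 df), and its ICC tolerance at the revised size falls from 0.149 to 0.089 (16 surgeons, normal).

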4.8.2 Analysis Plan

All data will be entered into REDCap, a secure research electronic data capture database (developed for the trial), and subsequently transferred to Stata for analysis. Initial examination of data will include descriptive statistics, frequency distributions, and histograms in order to identify outliers and missing data. All participants will be asked to indicate at T2 which

intervention they have received by being shown an image of each. Using this information, we will perform both an intention-to-treat and as-treated analysis.

4.8.3 Analysis Corresponding to Aim 1

Adapting the Decision Quality Instrument in Year 01.

We will use a two-step thematic analysis derived from descriptive phenomenology, assisted by the computer software ATLAS-ti. First, the transcripts will be coded to identify DQI items and instructions that require adaptation. In a second and more detailed analysis, the interview transcripts will be coded according to all the themes discussed in the interviews, including spontaneously emerging themes. Similar codes will be merged and subsequently grouped into families of codes and networks. Dual independent coding will be used for 100% of all interview transcripts, to ensure reliability of coding and to agree the themes and family of codes for all remaining interview transcripts. Discrepancies among raters will be discussed until agreement is reached.

Aim 1: Assess the comparative effectiveness of two effective encounter decision aids (Option Grid and Picture Option Grid) against usual care, on shared decision-making, decision quality, treatment choice and other direct outcomes in women, and differentially by SES.

We will first perform separate analyses for each follow-up period using linear and logistic regression models as appropriate for continuous (decision quality, SDM, quality of life, anxiety, decision regret, and IntegRATE) and binary (treatment choice) outcomes, respectively. The results will provide potentially valuable insights into how rapidly each intervention affects outcomes. Outcomes measured multiple times after T0 (anxiety, regret, decision quality, and financial toxicity) may also be analyzed using a longitudinal model. If the interventions are found to have an effect, a secondary analysis that adds predictors for the number of prior Option Grid and Picture Option Grid patients seen by the healthcare professional will examine whether there are physician learning effects under either intervention.

We will adopt a regression framework for all analyses as it allows seamless transition between basic analyses involving a single predictor (or two indicators corresponding to each intervention versus the comparator) and more complex analyses involving additional predictors (mediation variables, control covariates, time-trends, interaction terms or effect modifiers). Further, the regression framework allows clustering of observations due to repeated measurements on patients across time, nesting of health professionals within sites, and patients within health professionals, to be accurately accounted for using mixed-effect regression models¹¹⁷ or generalized estimating equations^{118,119}. Multiple comparisons will be accounted for using Scheffe's method¹²⁰.

The secondary outcomes (SDM, anxiety, integration of healthcare delivery, decision regret, quality of life and financial toxicity) have in excess of 10 levels and will be analyzed as continuous variables. To assess whether the results of each analysis are trustworthy, we will analyze the residuals to check if the assumptions of the model hold¹²¹. For treatment choice, a clearly defined binary variable based on medical record data, we will adapt the model to a logistic regression model.

As mentioned above, insurance status will be used to screen for higher and lower SES groups and invite participants into the study. It is an accepted proxy for SES¹⁵. At baseline, we will also collect information about median household income and highest educational attainment. For each included participant, we will check whether income and education confirm the initial screening allocation to higher or lower SES group or whether the patient belongs to the other group. The three measures of baseline socio-economic status: (1) insurance status, (2) highest educational attainment, and (3) median household income, will be analyzed separately for a multiple informants analysis¹²², or, provided they are not excessively collinear, we will enter them in the model together and test their combined effect. For income, we will use a poverty income ratio: the ratio of household income accounting for household size and poverty line published by the Census Bureau in the calendar year in which recruitment begins¹²³. To aid interpretation of our results, we will report the consequence of reassigning a patient from above median SES group to below median SES group, even if for added precision, it makes sense to base significance tests on continuous measures.

To gain insight into whether the Picture Option Grid and Option Grid will be more effective in certain subpopulations, we will add each SES measure and its interaction with the intervention indicator variables to the model. If the SES intervention interaction is non-significant, we will remove them from the model and test if the overall effect of SES is significant. Otherwise, we will perform stratified analyses of the interventions' effects by SES status.

4.8.4 Analyses Corresponding to Aim 2

Aim 2: Measure the effect of the Picture Option Grid on disparities in decision-making (decision quality, knowledge and shared decision-making) and treatment choice, and conduct an exploratory analysis of the mediation and moderation effects.

A logistic regression model will be used to test for differences in decision quality, knowledge, participation in SDM, and treatment choice between the Picture Option Grid group and the usual care and Option Grid groups, within subpopulations (higher SES versus lower SES). A reduction of disparity due to the interventions will be claimed if the effect of SES on outcomes is significantly smaller for the Picture Option Grid group than for the other two groups at follow-up. As for Aim 1, a linear regression model will be used for the decision quality analysis while an analogous set of other predictors will be included as covariates in the model. The assumptions of the models will be evaluated for adequacy using residual analysis and other model fit diagnostics¹²¹. Our exploratory mediation analyses seek to identify and explicate the mechanism or process that underlies the relationship between the Picture Option Grid and a dependent variable via the inclusion of a third explanatory variable, known as a mediator variable (e.g., knowledge, values, SDM). We are specifically interested in whether interventions operate through the mediator as opposed to directly affecting the outcome. We will perform these analyses even if the findings from Aim 1 and Aim 2 (hypothesis 1) are non-significant in order to determine whether the null effect was due to a null effect of the intervention on the mediator or a null effect of the mediator on the outcome. To determine the generalizability of these mechanisms and identify subpopulations for whom mediation is most pronounced, we will compare the mediation effects across different subgroups (e.g., higher SES versus lower SES).

The traditional and often-used approach to estimating mediation effects is the causal steps approach, which originated in Baron and Kenny (1986)¹²⁴. However, due to the limitations of that approach, we will estimate the mediation effect using the product of coefficients method¹²⁵. Standard errors will be evaluated using the bootstrap¹²⁶ or the PRODCLIN program¹²⁷. Software exists for sensitivity analysis to violations of sequential ignorability and other assumptions required for causality in mediation analyses^{128,129}. We will apply this software and any additional procedures available to our analyses in order to obtain the most robust and defendable results.

4.8.5 Analyses Corresponding to Aim 3

Aim 3: Explore strategies that promote the encounter decision aids' sustained use and dissemination using a theoretical implementation model.

We will use a framework analysis, guided by Normalization Process Theory (NPT)^{130,131}, having successfully used this approach previously^{63,101,132,133}. Observations and field-notes will be included in the analysis. Initial descriptive codes will be generated by two independent researchers based on the four NPT constructs. In-vivo coding will also be used to capture other naturally occurring exchanges. Categorical codes that group initial and in-vivo codes will be developed in a third round of coding. In addition, 100 photos of the interventions taken at T2 (approximately 50 of Option Grid and 50 of Picture Option Grid) will be included in the analysis to answer questions 1 and 2. Triangulation of data will also be performed.

NPT was developed to understand how complex interventions become implemented in routine healthcare settings⁹⁶. NPT is built around four theoretical constructs: 1) Sense-making: processes of individual and communal sense-making of a complex intervention regarding its use and value; 2) Participation: processes of 'cognitive participation' that promote or hinder users' buy-in and commitment to the intervention; 3) Action: processes of 'collective action' that determine or hinder whether the intervention is being used by all as intended; and 4) Monitoring: Processes of communal and individual appraisal of the effect of the intervention. We will use NPT as an analytical lens to consider the data collected according to our hypotheses and the following five questions: (1) how the interventions were perceived and used in and outside the clinical encounter (including with family and caregivers), (2) preferred ways for introducing and using the intervention in routine clinical settings, from several perspectives: patients, family, health professionals, administrators (3) perceived fit in clinic workflow as well as reported barriers and facilitators to routine integration, (4) other perceived patient-, physician- and system-level barriers and facilitators to routine use, and (5) perceived generalizability and feasibility in routine care.

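### Four outcomes have a T0 score, but Sections 4.8.3 and 4.8.4 do not specify adjustment for it

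*Combined protocol and SAP*

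**What the plan says.** Section 4.1.2 supports the choice of design by citing a source that favours a randomised experiment "with measurements of key variables pre- and post-interventions". Table 3 (Section 4.5.1) and Table 4 (Section 4.7.6) then schedule four outcomes at T0 and again later:

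- "Knowledge – validated 5-item DQI knowledge subscale": T0, then within the full DQI at T2 and T3.
- "Anxiety – validated 8-item PROMIS anxiety short form": T0, T2, T3 and T4.
- "Quality of life – validated 6-item EQ-5D-5L": T0 and T4.
- "Integration of health care delivery – validated 4-item IntegRATE": T0 and T4.

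The full primary instrument has no T0 administration: "The DQI, designed to be administered post-decision, will be assessed at T2 and T3".

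For Aim 1, Section 4.8.3 states: "We will first perform separate analyses for each follow-up period using linear and logistic regression models as appropriate". A longitudinal model is optional and is confined to outcomes measured more than once after T0, so quality of life and IntegRATE fall outside it. The regression framework starts from "basic analyses involving a single predictor (or two indicators corresponding to each intervention versus the comparator". The same sentence goes on to allow further predictors, including covariates for control, without naming any. Section 4.8.4 says that a set of predictors analogous to Aim 1 will enter as covariates, again unnamed. The baseline variables that do receive a stated role are the SES measures (Section 4.8.3) and the candidate effect modifiers (Section 4.8.8).

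**The concern.** The T0 scores are collected, but nothing says that they will be used. Whether to adjust, and for which scores, is therefore left to be settled after the data are seen.

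This matters more here than in a patient-randomised trial of the same size. Arms are allocated to surgeons, about five per arm, so differences in case-mix between surgeons do not average out well. A T0 score of the same outcome is usually the most useful single covariate. Leaving it out gives up precision, and if an imbalance does occur, the reported effect is not conditioned on it. Knowledge is affected twice, because it is an outcome in both Aim 1 and Aim 2 (Section 3.2). For Aim 2, Section 4.8.1 already concedes that power is unlikely to reach 80% with 600 women.

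**Working it through.** **Inputs from the documents**

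- Section 4.8.1: 600 women (previously 1,100), four physicians at each of four sites (16), ICC 0.05, 20% attrition, DQI difference 9.34, SD 12.00, two-sided 0.05.
- Section 4.1.2: three to five clinicians per site, so 12 to 20 in total. Per arm this is 16/3 = 5.33, with a range of 4.0 to 6.7.

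**Assumptions**

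- ICC 0.05 holds for each of the four outcomes. The protocol states it only for the DQI.
- The T0-to-follow-up correlation is 0.3 to 0.7. The documents give none. The only related figure is the 4-week retest ICC of 0.70 for knowledge (Section 4.5.1).

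**Reproducing the plan's own figure.** At 1,100 women, 880 are analysed, or m = 880/16 = 55 per surgeon. The design effect is 1 + 54 × 0.05 = 3.70. Per arm, 293.3/3.70 = 79.3 effective women. The SE is 12 × √(2/79.3) = 1.906, and 9.34/1.906 = 4.90. Power is Φ(4.90 − 1.96) = 0.998, which agrees with the stated figure of more than 99.8%. The printed design effect of 4.04 corresponds to 10% attrition rather than 20% (m = 61.875, and 1 + 60.875 × 0.05 = 4.04). That is a separate matter.

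**The same method at 600.** 480 are analysed, 160 per arm, m = 30. The design effect is 0.95 + 30 × 0.05 = 2.45. The SE is 12 × √(2 × 2.45/160) = 2.10, and unadjusted Aim 1 DQI power is Φ(9.34/2.10 − 1.96) = 0.994. With a t test on surgeon-level degrees of freedom it is 0.975.

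**Size of a chance T0 difference between two arms, in SD units**

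- 16 surgeons: √(2 × 2.45/160) = 0.175, so a 95% range of about ±0.34. The probability of exceeding 0.2 SD in either direction is about 25%.
- If patients had been randomised: √(2/160) = 0.112.
- 12 surgeons (m = 40, design effect 2.95): √(2 × 2.95/160) = 0.192. 20 surgeons (m = 24, design effect 2.15): √(2 × 2.15/160) = 0.164.
- 16 surgeons with only 5% loss, the missing-data level expected in Section 4.8.7: 0.170.

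**Effect of adjusting.** Let r_w be the within-surgeon correlation and r_b the surgeon-level correlation. The variance factor goes from (1 − ICC) + m·ICC = 0.95 + 1.50 = 2.45 to 0.95(1 − r_w²) + 1.50(1 − r_b²). The unadjusted detectable difference at 80% power is 2.80 × 0.175 = 0.49 SD.

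| r | Factor, within only (r_b = 0) | Variance cut | Detectable | Factor, both levels (r_b = r_w) | Variance cut | Detectable |
|---|---|---|---|---|---|---|
| 0.3 | 2.36 | 3.5% | 0.48 SD | 2.23 | 9% | 0.47 SD |
| 0.5 | 2.21 | 9.7% | 0.47 SD | 1.84 | 25% | 0.43 SD |
| 0.7 | 1.98 | 19% | 0.44 SD | 1.25 | 49% | 0.35 SD |

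The range is wide because 1.50/2.45 = 61% of the variance of a surgeon mean lies between surgeons, and the surgeon-level correlation is unknown.

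**Shift when an imbalance occurs.** If the correlation is the same at both levels, a one-SE T0 difference moves the unadjusted contrast by 0.175r, which is 0.05, 0.09 or 0.12 SD for r = 0.3, 0.5 or 0.7.

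**Aim 2.** Section 4.8.1 notes that SES varies within physician. If a surgeon's effect is the same in both SES strata, it cancels from the disparity contrast. The variance saving for knowledge then approaches r_w², which is 9%, 25% or 49%.

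**The case against.** The plan does not rule out baseline adjustment. Section 4.8.3 allows covariates, Section 4.8.4 says that covariates will be included, and Section 4.8.7 provides for imputing missing baseline data, which is consistent with baseline variables entering models. A reader might infer from the basic model that T0 scores will be left out. The documents do not support that reading. What stands is that no T0 score is named anywhere, so adjustment is permitted but not pre-specified.

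A reader might also infer that the unadjusted analysis is biased. It is not: chance imbalance between randomised surgeons is random error, and the SE of a correctly clustered mixed model or GEE already reflects it. Adjustment gives a smaller SE and an estimate that is conditional on the imbalance that occurred.

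The link to the primary outcome is limited. The DQI total has no T0 value, only its knowledge score does, and knowledge is not in the list of outcomes that follows the sentence on separate analyses. The other three outcomes are secondary.

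The size is also soft. A retest ICC of 0.70 is a reliability figure, and T0 and follow-up knowledge are separated by a consultation meant to change knowledge, so 0.70 is closer to a ceiling than to an expected value. Nothing in the documents supports a particular correlation for anxiety, EQ-5D-5L or IntegRATE, and the last two run from T0 to 12 weeks after surgery. These points stand, which is why the result is given as a range that starts at 3.5%.

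**Conclusion.** The point holds as a gap in specification with an almost free remedy. Four outcomes have a T0 score that no planned model names. The direction of the gain is secure. Its size is a variance reduction of 3.5% to 19% (correlation within surgeons only) or 9% to 49% (both levels), given 600 women, 16 surgeons, 20% attrition, ICC 0.05 for each outcome and correlations of 0.3 to 0.7. The chance T0 difference of 0.175 SD per standard error depends on the same ICC and surgeon count, but not on the correlations.

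Two stronger conclusions are tempting and should not be drawn. The first is that adjustment is needed to recover Aim 1 power after the cut to 600: on the protocol's own assumptions, DQI power stays at 0.994, or 0.975 with surgeon-level degrees of freedom. The second is that the imbalance can be expressed in DQI points by using SD 12: that SD belongs to the DQI, which has no T0 total to be imbalanced. The case rests on precision and conditional protection for the four outcomes, including knowledge in Aim 2, where the protocol itself expects power to be short.

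**What to change.** - State in Sections 4.8.3 and 4.8.4 that the main mixed model or GEE for knowledge, anxiety, quality of life and IntegRATE includes that outcome's own T0 score as a covariate. Report the model without it as supportive.
- Use only T0 scores taken before the consultation. Section 4.7.4 lets some women complete T0 afterwards, when the decision aid may already have been used. Treat those scores as missing and handle them with the multiple imputation already planned in Section 4.8.7.
- Two additions may be listed as sensitivity analyses. One adjusts the other DQI scores for T0 knowledge; no correlation is stated to support this as the main model. The other adds the surgeon mean of T0. It uses one of roughly ten surgeon-level degrees of freedom (16 surgeons − 1 intercept − 2 arm terms − 3 site terms = 10), or one of six if only 12 surgeons take part.

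The cost is SAP wording, agreed before the outcome data are analysed. The scores are already collected, so no new data, visits or patients are needed.
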